1.5.2 Anticipated Risks

ONT sequencing will be utilized alongside current SCs. We will use SC to ensure that the care patients receive will be no worse than current practice. In other words, culture will ensure that ONT only improves patient care and outcome. In the event that ONT results and culture assessment contradict, the care plan will prioritize the results of standard culture in the event of treatment failure (Table 3). The risks associated with participation in this study are no greater than for those patients not on the study also undergoing identical operations. The only therapeutic interventions this trial includes is alteration or cessation of postoperative antimicrobial therapy based on either ONT or SCs. In order to minimize any theoretical risks in the ONT arm, such as missed microbial species and/or antibiotic resistance phenotype or ineffective antibiotic regimen, SC data will be utilized in both arms and antibiotic therapy will be adjusted if SCs suggest broader coverage (Table 3). There will be no alteration in the standard clinical postoperative care of patients in this study.

Table 3: Incorporation of ONT results in clinical management decisions

ONT Result	Clinical management decision
A negative ONT result	Discontinue antibiotics after 24 hours of peri-operative coverage
A positive ONT result for a single pathogen typical of biliary or gastrointestinal flora	Adjust and/or narrow antibiotic therapy to cover single pathogen. If single pathogen deemed clinically insignificant (ie. lactobacillus), discontinue antibiotics after 24 hours of peri-operative coverage.
A positive ONT result for multiple pathogens	Adjust and/or narrow antibiotic therapy to cover all pathogens, excluding those deemed clinically insignificant. If all pathogens are considered clinically insignificant, discontinue antibiotics after 24 hours of peri-operative coverage.
A positive ONT result positive for rare or unexpected flora	Adjust and/or narrow antibiotic therapy to cover rare or unexpected flora, excluding those deemed clinically insignificant.
ONT results different from SC	Adjust and/or narrow antibiotic therapy to cover pathogens found in ONT results, excluding those deemed clinically insignificant. SC results to only be considered in the event of treatment failure with antibiotic therapy targeted towards ONT results.

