At our institute the current standardized approach is administer a perioperative prophylaxis course of ceftriaxone plus metronidazole 60 minutes prior to surgery (Figure 1). Antibiotic treatment is continued for 5-days postoperatively for patients undergoing pancreatic head resection, and the selection and duration of this specific broad-spectrum prophylactic regimen is based on recommended surgical guidelines and our own historical SSI culture data⁴³. During surgery, bile swab and aspirate samples are collected and transferred to the Pathology lab to undergo standard bile cultures and AST. If the bile cultures are eventually negative for microbial growth, the patient will be taken off the broad-spectrum antibiotics following completion of the 5-day prophylactic regimen (Figure 1). If the bile cultures are positive, then antibiotic treatment will be extended for 10 days, and therapy is tailored based on organisms and resistances identified in the bile cultures (Figure 1). Introduction of this approach in 2014 resulted in significant decrease in hospital stay, reduced the need for interventional radiology procedures, and decreased the risk of postoperative pancreatic fistula grade⁴³. Within the first year of introduction, our approach significantly decreased inpatient cost of care, decreased the total 30-day costs, and saved a total of \$1.1 million, in addition to improving patient outcome⁴³.

[figure not shown]

Figure 1: Schematic diagram of the current standardized perioperative prophylactic antibiotic treatment plan for patients undergoing total pancreatectomy and pancreaticoduodenectomy at our institution.

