1.4 Clinical Data to Date

This study will use data that has been collected under the following research study: "Comparative Analysis of Bile Microorganisms in Patients Undergoing Major Hepatobiliary Operations", IRB# 19-011419 and published in two peer-reviewed journals^{44,48}. In brief, these studies involved analysis of intraoperative bile aspirate samples collected from 42 patients undergoing pancreatic head resection (total pancreatectomy, n = 9; pancreaticoduodenectomy, n = 33) at Mayo Clinic, Rochester (see Table 1 for patient characteristics). Metagenomic ONT sequencing was performed on bile aspirates to identify microbial species (bacterial, fungal) and antibiotic resistance genes. Sequencing results were then compared to bile cultures performed as part of Mayo Clinic's standard of care clinical practice to determine how ONT sequencing compared to current 'Gold Standard' culture practices^{44,48}.

To determine the optimum ONT protocol for detection of microbial species and antibiotic resistance genes present in the bile aspirates, different methods of DNA extraction, use of host DNA depletion, and use of different AMR gene databases were evaluated⁴⁸. In total, intraoperative biliary microbes were detected in 54.7% (23/42) of patients undergoing total pancreatectomy or pancreaticoduodenectomy using SC techniques. This included 35.7% (15/42) of patients with positive bacterial cultures, 2.4% (1/42) of patients with positive fungal cultures, and 16.7% of patients with positive fungal and bacterial cultures. The male sex, use of biliary instrumentation, and performance of vascular reconstruction during surgery was significantly correlated with the detection of biliary microbes.

Table 1: Clinical characteristics of patients included in our preliminary study

Clinical feature	Total	Biliary microbes ⁺	Biliary microbes ⁻	P value
Age, mean (IQR)	61 (22 - 71)	66.3 (46.3 - 81.3)	58.0 (18 - 82.6)	0.0858
BMI, mean (IQR)	26.4 (19 - 40.4)	26.3 (19 - 40.4)	26.4 (19.7 - 36.2)	0.9295
Sex, % male (n)	54.8 (23)	38.1 (16)	16.7 (7)	0.0375
Surgery indication, % (n)				0.892
Pancreatic ductal adenocarcinoma	45 (29)	50 (21)	19.0 (8)	
Intraductal Papillary Mucinous Neoplasm	7.1 (3)	0 (0)	7.1 (3)	
Neuroendocrine tumors	11.9 (5)	2.4 (1)	9.5 (4)	
Other	11.9 (5)	2.4 (1)	9.5 (4)	
ASM Score, mean (IQR)	2.6 (1 - 4)	2.7 (2 - 4)	2.5 (1 - 3)	0.1874
Type of surgery				0.9716
Total pancreatectomy, % (n)	21 (9)	11.9 (5)	9.5 (4)	

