Pancreaticoduodenectomy, % (n)	79 (33)	42.9 (18)	35.7 (15)	
Biliary instrumentation, % (n)	52 (22)	52.4 (22)	0 (0)	<0.0001
Vascular reconstruction, % (n)	38 (16)	31.0 (13)	7.1 (3)	0.0079

BMI, body mass index; IQR, interquartile range

Comparison of our optimized ONT sequencing protocol SC results revealed that our ONT protocol had identified 100% of biliary microbial contamination cases, detected 75% of cultured bacterial species and 76% of cultured fungal species, and predicted 81% of antibiotic resistance phenotypes observed using SC results ^{44,48}. With regards to detection of common biliary pathogens ^{3,54-57}, our ONT protocol improved detection of biliary candidiasis, detected 100% of cases of biliary *Escherichia coli* and biliary *Klebsiella*, and detected 83% of biliary *Enterobacter*, 76.5% of biliary *Enterococcus*, 93.8% of biliary *Streptococcus*. However, ONT did not detect one case of *Pseudomonas* infection and one case of *Staphylococcus aureus*, indicating as proposed in this study that SC techniques should be run alongside ONT protocols to ensure that no microbial species are missed. As for detection of pathogens of high clinical concern (i.e. ESBL, CRE species), ONT similar detection rates compared to SC, and potentially improved detection of *E. coli*, *K. oxytoca*, *K. pneumoniae*, and *Citrobacter freundii*. Overall, ONT improved detection of microbial species (particularly with regards to anaerobic species and fungal species) and predicted a significantly higher number of antibiotic resistance phenotypes than were identified using SC. Significantly, the results turnaround for ONT sequencing was just 14 hours compared to an average turnaround time of 98 hours for SC. On average, it took 4.8 days (range = 1 – 15 days) to complete microbial identification and an additional 2 days (range = 0 – 9 days) to complete AST for the culture positive samples. Delays greater than 5 days in completing microbial identification occurred in samples with multiple aerobic species of the same genus (*Enterococcus* spp., *Klebsiella* spp., *Streptococcus* spp.), anaerobic species (*Schaalia (Actinomyces) turicensis*, *Finegoldia magna*, *Veillonella* sp., *Actinomyces johnsonii*, *Parvimonas micra*), and/ or fungal species *Saccharomyces cerevisiae*, *Candida* spp.), and on average, optimal antimicrobial therapy was delayed for 7 days. Use of a test that would enable microbial identification and prediction of AMR phenotypes within 24hrs post-surgery, would, therefore, have significantly shortened the delay in patients receiving optimized tailored antimicrobial therapy post-surgery.

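### Section 1.5.2 says culture will ensure care no worse than current practice, but a false-negative ONT result stops antibiotics at 24 hours and no rule sends that discordance to the DSMB

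*Combined protocol and SAP*

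**What the plan says.** Section 1.5.2 gives two assurances: "We will use SC to ensure that the care patients receive will be no worse than current practice", and "The risks associated with participation in this study are no greater than for those patients not on the study". It names missed species or resistance in the ONT arm as a theoretical risk and answers it with culture: "antibiotic therapy will be adjusted if SCs suggest broader coverage".

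The comparator is set in Section 1.1: "Antibiotic treatment is continued for 5-days postoperatively for patients undergoing pancreatic head resection". Under General Design, a positive culture extends treatment to a full 10-day course. Tables 3 and 5 stop antibiotics after 24 hours when ONT is negative. On timing, Section 1.4 reports that "the results turnaround for ONT sequencing was just 14 hours compared to an average turnaround time of 98 hours for SC".

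Four texts describe what happens when culture contradicts ONT, and they differ:

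- General Design, description of Arm 2: a positive culture guides therapy in place of ONT.
- Section 1.5.2, text: therapy is adjusted if culture suggests broader cover.
- General Design, text before Table 5: on growth, the clinician has the option of returning to standard practice.
- Section 1.5.2, text, and last row of Tables 3 and 5: culture is prioritised, or considered at all, only on treatment failure.

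Confidence in the early stop rests on the pilot. Section 1.4 says that "our ONT protocol had identified 100% of biliary microbial contamination cases", and General Design restates this as no false-negative calls. The denominator comes from "intraoperative biliary microbes were detected in 54.7% (23/42) of patients". No interval is given.

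**The concern.** The early stop creates one failure mode that current practice does not have: a patient with contaminated bile who is taken off antibiotics on a wrong negative result. Culture is the safety net, but on average it reports days after the stop. It can shorten the gap but cannot give back hours already lost. The wording in Section 1.5.2 excludes any such gap, and the minimal-risk statement in General Design leans on it.

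Two further points add to this. The evidence that the failure mode does not occur is a small zero numerator. And if it does occur, the affected patients would be few, so comparisons between arms are a poor way to see them.

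**Working it through.** **1. Hours of cover lost.** Clock from surgery (assumption). Stop at 24 h; standard cover 5 × 24 = 120 h; culture-positive course 10 × 24 = 240 h. Loss of 5-day cover = min(time culture is acted on, 120) − 24, floored at 0.

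| Culture acted on at | Source of the time | Loss |
|---|---|---|
| by 24 h | first plate reading after at least 16 h (Supplement S2) | 0 h |
| 98 h | average turnaround (Section 1.4) | 98 − 24 = 74 h |
| 4.8 days = 115.2 h | mean time to identification (Section 1.4) | 115.2 − 24 = 91.2 h |
| 120 h or later | end of 5-day course | 120 − 24 = 96 h |
| never | 10-day course (General Design) | 240 − 24 = 216 h |

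Standard prophylaxis contains no antifungal (Section 1.1), so a missed *Candida* loses no antifungal cover.

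**2. What the pilot excludes.** 0 misses in 23 culture-positive patients. Exact two-sided 95% upper limit: 1 − 0.025^(1/23) = 14.8%. The same series was used for development work: "different methods of DNA extraction, use of host DNA depletion, and use of different AMR gene databases were evaluated".

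**3. Misses compatible with that.** Culture-positive patients in Arm 2: 0.54 × 70 = 37.8, about 38 (Section 6.1).

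| Miss rate | Expected misses | Chance of none |
|---|---|---|
| 2% | 0.02 × 38 = 0.8 | 0.98^38 = 46% |
| 5% | 0.05 × 38 = 1.9 | 0.95^38 = 14% |
| 14.8% | 0.148 × 38 = 5.6 | 0.852^38 = 0.2% |

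For scale, Section 6.1 plans on 77% ONT positivity, so about 0.23 × 70 = 16 Arm 2 patients are ONT-negative. At the upper limit, 5.6/16 is about a third of those calls.

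**4. Whether arm comparisons would show it.** Take the pilot 30-day SSI rate of 21.4% in both arms (0.214 × 70 = 15) and, as an extreme, let every missed patient have an SSI that would not otherwise occur. Two-sided tests at the final look:

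| Arm 2 v Arm 1 | Extra SSIs | Fisher p | Chi-square p (uncorrected) |
|---|---|---|---|
| 17/70 v 15/70 | 2 | 0.84 | 0.69 |
| 21/70 v 15/70 | 6 | 0.33 | 0.25 |
| 26/70 v 15/70 | 11 | 0.063 | 0.041 |
| 27/70 v 15/70 | 12 | 0.042 | 0.027 |

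So p<0.05 needs 11 extra SSIs (chi-square) or 12 (Fisher), about twice the upper-end number of misses. Adding the two later pilot SSIs (11/42 = 26.2%, about 18 of 70) leaves these thresholds unchanged: 29/70 v 18/70 gives chi-square p=0.049, and 30/70 v 18/70 gives Fisher p=0.0496.

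The chance of Fisher p<0.05 with Arm 2 worse at the final look is 1.6% with no extra SSIs, 3.8% with 1.9 and 14.1% with 5.6. With looks every two weeks (3,000 simulated trials, even accrual, outcome known at once), the chance of ever crossing is about 6%, 11% and 26–27%. Part of that is the false-alarm rate of repeated looks.

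**5. Other routes to the DSMB.** Patient Follow-up and Safety Monitoring has daily inpatient and weekly post-discharge event monitoring, SAE reports to the IRB, and stopping for any other safety issue the DSMB identifies. Section 7.1 treats adverse events that cause or prolong hospitalisation as UADEs, and Section 7.1.3 copies UADE forms to the DSMB. The monitoring and the forms respond to harm, and the stopping provision depends on the DSMB's own review. Section 5.3 captures and compares culture and ONT results but sets no reporting step. Nothing is triggered by an ONT-negative, culture-positive pair.

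**The case against.** The plan is more candid and better monitored than the word *ensure* suggests. Section 1.4 discloses a missed *Pseudomonas* and a missed *Staphylococcus aureus*, Section 1.5.2 names missed species as a risk, and General Design hedges because the technology is new. SSI is one of nine stopping criteria in Table 7, so the detection figures above cover only part of the monitoring. The upper-end count would mean that about a third of negative calls were wrong, which the interval permits but which is far from the observed record. All of this stands, and it limits the size of the point. It does not supply the missing guarantee or a trigger on discordance.

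Stronger readings are tempting, and the documents do not support them:

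- *Lost cover causes SSI.* No data here link hours off antibiotics to infection, and with a background rate near 21% a single SSI after a missed call cannot be attributed to it.
- *The assay misses 15% of contaminated patients.* That is a confidence limit; the observed count is zero. The missed *Pseudomonas* and *S. aureus* are misses of organisms, reported alongside detection of every contaminated case.
- *Culture is ignored for ONT-negative patients until treatment fails.* The last row of Tables 3 and 5 is worded for therapy targeted at ONT findings, so its reach to a patient on no antibiotics is arguable.
- *The DSMB would never see such a case.* It could, through a UADE form or its own enquiry, but the first needs harm, and a risk already named in Section 1.5.2 may not count as unanticipated.

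**Conclusion.** The point holds as a mismatch between a stated safety property and the design, together with a gap in case reporting. Culture limits the loss after a false-negative call: about 0 to 96 hours of the 5-day cover, 74 at the average turnaround, and 216 hours against the 10-day course if care is never reverted. It cannot ensure there is no loss, and the four rescue texts do not agree on what the clinician must do. The pilot is compatible with 0 to about 6 such patients in Arm 2, possibly none. Arm-level SSI tests would need about 11 to 12 extra infections at the final look, so they are unlikely to reveal harm on that scale.

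The hours assume a clock from surgery and a stop at exactly 24 hours. The counts assume 54% culture positivity in 70 patients. The detection figures assume a 21.4% SSI rate in both arms and the extreme that every miss produces an SSI. Sample size, endpoints and analysis are unaffected. The change is worth making because it alters trial conduct at the one place where the early stop can go wrong.

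**What to change.** 1. In Section 1.5.2 and in the paragraph before Table 5, say that culture limits but does not remove the risk of lost cover after a false-negative ONT result. Give both figures: 0 to 96 hours of the 5-day course, and up to 216 hours of the 10-day course if care is not reverted. Cite the pilot as 0 of 23 missed, exact 95% upper limit 14.8%.
2. Make the Arm 2 rule in General Design (a positive culture guides therapy) the single rescue rule for ONT-negative patients, and align the other three texts with it. Rewording the risk section alone would leave the clinician without a clear instruction.
3. Report every ONT-negative, culture-positive case to the DSMB when growth is first reported, with hours off antibiotics and whether care was reverted. Add SSI outcome when known. Treat this as a safety signal for review, in addition to the existing checks, and not as proof of cause.

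The cost is text edits and one listing from data already captured under Section 5.3. The assay statement becomes less favourable, and the DSMB handles 0 to about 6 single-case notices over the trial.

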1.5.3 Potential Benefits

Potential benefits associated for patients who participate in this study include:

- Earlier diagnosis of biliary microbial contamination
- Earlier targeted antimicrobial therapy post-surgery

- Reduces window of opportunity for pathogenic species to propagate and cause infection
- Reduced risk of SSIs
- Potential candidate for earlier chemotherapy
- Earlier cessation of unnecessary antimicrobial therapy following negative result of biliary aspirates
 - Cost saving from stoppage of IV antibiotic administration
 - Potential candidate for earlier chemotherapy
 - Reduced gut microbiome disruption and decreased risk of adverse events following antibiotics
- Wider impact – reduction of broad-spectrum antibiotic usage, subsequently improving antibiotic stewardship and avoid antibiotic associated complications

The technology will improve antibiotic stewardship by rapidly identifying which patients require antimicrobial therapy, reducing time spent on broad-range antimicrobial therapy, and decreasing the risk of emerging resistance by ensuring that patients who do require antimicrobial therapy are on an optimal treatment regimen. Patients will directly benefit through early diagnosis of biliary microbial contamination. This will enable patients who require antimicrobial therapy to receive early targeted antimicrobial therapy post-surgery, potentially reducing the risk of infection by decreasing the window of opportunity for pathogenic species to propagate. Patients who do not require antimicrobial therapy will benefit by being taken off therapy earlier, reducing patient exposure to broad-spectrum antibiotics and the risk of adverse events and long-term health impacts associated with unnecessary antimicrobial therapy.

The data from this study will provide an important scientific characterization of the biliary flora in patients undergoing pancreatic head resection. Given the high risk of infection, better characterization of these microbes using untargeted approaches will provide a more complete picture of potential pathogen risks on a population level. The scientific knowledge gained in this study may influence future studies and therapeutic possibilities, especially with regard to underassessed species such as fungi and obligate anaerobes.

1.6 Anticipated Duration of the Clinical Investigation

The anticipated duration of this study is 2 years. Direct participation for participants lasts until surgical specimens have been obtained. Additional follow-up data will be collected from the medical record for up to 90 days following the procedure.

2 Study Objectives

2.1 Hypothesis:

The use of ONT sequencing, a novel metagenomic technique, will result in faster identification of organisms from intra-operatively collected bile samples and allow for early treatment of biliary microbial contamination. Supplementing SC with ONT sequencing data will allow patients to be treated earlier in the post-operative setting with tailored antibiotics, which will reduce the rate of biliary microbial contamination related SSIs in patients undergoing pancreatic head resection as compared to SC alone.

2.2 Primary Objective

To improve antibiotic stewardship (reducing duration of peri-operative prophylactic antibiotic regimen, reducing administration of broad-spectrum antibiotic) by providing surgical team with rapid ONT sequencing data in the early post-operative setting.

Success Criteria: Significantly reduced antibiotic regimen duration and use of broad-spectrum antibiotics, corrected for key co-variates ($p<0.1$).

2.2 Secondary Objective

To reduce the cost of care through reduction in SSI and improved antibiotic stewardship.

Success Criteria: Significantly reduced rates of SSI and reduced total hospital costs, corrected for key co-variates ($p<0.1$).

2.1 General Design

This will be a prospective 1:1 randomized controlled trial with the following study arms:

Arm 1: Patient Group 1

Standard Care Only. Patients will undergo intra-operative bile aspiration (as is routinely performed) with SC of the aspirate. All patients will receive standard prophylactic antibiotics according to practice standards and will be continued for up to 5 days as is routine. If bile cultures are positive, antimicrobials will be continued for a complete 10-day course of antibiotics (Figure 2).

Arm 2: Patient Group 2

Standard Care + ONT. Patients will undergo intra-operative bile aspiration (as is routinely performed) with standard cultures AND ONT sequencing of the aspirate. All patients will receive standard prophylactic antibiotics according to practice standards. ONT sequencing results will be made available to providers through electronic medical record (EMR) and team electronic notifications. Patients with negative ONT results will be taken off the standard prophylactic antibiotics and patients with positive ONT results will have antimicrobial therapy adjusted according to ONT sequencing results. However, if SCs are positive or suggest alternative/broader coverage then these results

will guide therapy and not ONT results. If bile cultures are positive, antimicrobials will be continued for a complete 10-day course of antibiotics (Figure 2).

[figure not shown]

Figure 2: A schematic diagram of our proposed study to investigate the use of Oxford nanopore sequencing to detect and characterize biliary microbial contamination

The study will include patients undergoing elective pancreaticoduodenectomy or total pancreatectomy for any clinical indication. Patients will be excluded from the study if they are < 18 years of age, enrolled in any similar clinical trials involving use of peri-operative antibiotics, are undergoing distal pancreatectomy, or undergoing emergency total pancreatectomy or emergency pancreaticoduodenectomy (Table 4). Following recruitment to the study, patients will be randomly assigned intraoperatively/post-operative to either the control group (Arm 1) or the interventional group (Arm 2). We will use stratified randomization with age (below 65 years vs 65 years and above), sex, operation type (pancreaticoduodenectomy vs total pancreatectomy), biliary stenting (yes vs no), and patient ASA score as stratification factors.

Table 4: Patient inclusion and exclusion criteria for the clinical trial

Inclusion Criteria	
 • > 18 years of age • Scheduled for elective total pancreatectomy or pancreaticoduodenectomy
Exclusion Criteria	
 • < 18 years of age

	
• Emergency total pancreatectomy or pancreaticoduodenectomy• Patients scheduled for distal pancreatectomy• Women who are pregnant• Patients without the cognitive capacity to consent• Patients enrolled in similar clinical trials involving use of perioperative antibiotics
--	--

Bile will be collected via bile duct aspiration. Bile aspiration will be performed with a 16-gauge needle and 3 cc syringe prior to bile duct division (Figure 3), and aspirated material will be aseptically transferred into sterile aerobic and anaerobic transport vials. Samples will be concurrently transported to the Pathology lab and the microbiome lab to undergo SC techniques and ONT sequencing, respectively. Standardization of bile collection and surgical procedure will be assured as all surgeries will be performed by the same lead surgeon, [name]. Surgical variables that have been associated with increased SSI risk will be recorded. This will include patient sex, age, BMI, ASA score, the volume of blood loss, whether the patient had a biliary stent inserted prior to surgery, closure technique, and whether vascular reconstruction was performed during surgery.

[figure not shown]

Figure 3: Collection of intraoperative bile aspirate during pancreatic head resection (total pancreatectomy, pancreaticoduodenectomy)

SCs obtained from intraoperative bile aspiration for both study arms will be performed in compliance with clinical standards. This is routinely performed by the Pathology lab and no changes to these protocols are necessary (see Supplementary Materials S1 – S6) for culture methods and AST protocols). Results will be reported in the EMR which will be accessible by the clinical team, as is the current clinical practice. ONT sequencing for those assigned to Study Arm 2 will be performed on a 1cc liquid bile sample collected fresh from the operating room after specimen release from the Pathology lab. Approval from our institutional TRAG

(Tissue Request Acquisition Group), will be requested for managing of intraoperative samples and will notify the study team of sample receipt. After collection, microbial DNA will be extracted and sequenced in preparation for reading per protocols^{44,48}. In brief, Porechop and BBMap will be used to remove adaptor sequences and low complexity reads. The filtered reads will then be aligned using Centrifuge in order to determine species identification. Bile aspirates will be declared microbial positive when 500 or more microbial reads are detected. Additionally, 50 reads per million (RPM) ratio (RPM-r), defined as $RPM-r = RPM_{sample} / RPM_{negative\ control}$, will be used as a minimum threshold to reduce biases caused by different sequencing depth and mitigate concerns regarding potential microbial contamination, as described in previous studies^{47,73,78,79}. Relative abundance of the microbial species detected will then be determined and high abundant species (species with a relative abundance greater than 1%) will then be reported to the care team. The sequenced reads will also be used to identify acquired chromosomal AMR genes and putative AMR phenotypes using ResFinder 4.1⁵¹. A minimum coverage of 95% and a minimum sequence identity of 95% will be used, and predicted phenotype and source organism of the identified AMR gene will be reported to the care team. To ensure that no potential resistance phenotypes are missed we will also use the PlasmidFinder and CARD tools with the default settings to check for any plasmid-acquired AMR phenotypes. This will be a critical step as CRE and ESBL genes are located on plasmids. However, due to these genes being located on plasmids, use of PlasmidFinder and CARD will not be used to declare presence of CRE- and/or ESBL-organisms but instead inform the Surgical Clinical Pharmacy and the Pathology laboratory about their potential presence in the patient sample.

After sequencing data is gathered, samples will be destroyed. The data results from the ONT sequencing testing will be entered into EMR as a research clinic note for documentation and results will additionally be emailed to the medical providers on the care team. Decisions on antibiotic regimen will be made with the assistance of Surgical Clinical Pharmacy with changes in regimens as deemed appropriate based on standard cultures and ONT results, as described in Table 5. A negative ONT result will result in discontinuation of perioperative antibiotics after 24 hours while a positive ONT result will be used to guide early targeted antibiotic therapy (Table 5). With regards to early discontinuation of antibiotics, we are confident that this will not adversely impact patient care as our preliminary data demonstrated that ONT resulted in no false negative calls. However, as this is a new technology, SC will be performed alongside ONT, and if microbial growth is detected in the cultures, the clinician will have the option of reverting patient care to current standard of practice. This option will also be available in the event of treatment failure in patients with positive ONT results (Table 5).

Given that currently clinically available tests will be available to the care team with the additional ONT sequencing as supplemental data there will be minimal risk to subjects participating in this study.

Table 5 Incorporation of ONT results in clinical management decisions

ONT Result	Clinical management decision
A negative ONT result	Discontinue antibiotics after 24 hours of peri-operative coverage

A positive ONT result for a single pathogen typical of biliary or gastrointestinal flora	Adjust and/or narrow antibiotic therapy to cover single pathogen. If single pathogen deemed clinically insignificant (ie. lactobacillus), discontinue antibiotics after 24 hours of peri-operative coverage.
A positive ONT result for multiple pathogens	Adjust and/or narrow antibiotic therapy to cover all pathogens, excluding those deemed clinically insignificant. If all pathogens are considered clinically insignificant, discontinue antibiotics after 24 hours of peri-operative coverage.
A positive ONT result positive for rare or unexpected flora	Adjust and/or narrow antibiotic therapy to cover rare or unexpected flora, excluding those deemed clinically insignificant.
ONT results different from SC	Adjust and/or narrow antibiotic therapy to cover pathogens found in ONT results, excluding those deemed clinically insignificant. SC results to only be considered in the event of treatment failure with antibiotic therapy targeted towards ONT results.

Databases Used

For the analysis of our endpoints, we are relying on sequence homology for two main tasks, mainly, (1) the identification of species and (2) identification of AMR phenotypes. For species identification, we use the refseq genome database (downloaded on 12/18/2020) with all data from the following higher order taxa groups included: human, protozoa, viral, bacterial, and fungal. For the identification of AMR phenotypes, we use the ResFinder database (downloaded on 06/04/2021, version 4.1) which contains the acquired chromosomal resistance genes, ensuring we know which species is carrying a given resistance gene. For plasmid AMR gene identification, we will use the PlasmidFinder-specific database (downloaded on 7.14.2021/version 2.0.1) and the CARD data (downloaded on 07/07/21, version CARD 2020). These databases undergo regular updates since they were first developed. To ensure the analysis remains consistent throughout the study, databases will not be updated for the duration of the study. In the unlikely event that we require a software/ database update in order to run these tools (compatibility issues with future institutionally required OS update, inability to restore databases from archives after computational disaster), we will validate any newer versions of the database and/or algorithms using the data and culture gold standards from our published study and recently collected data and will only proceed if we have comparable performance in accuracy for species and AMR identification.

Patient Follow-up and Safety Monitoring

Direct study participation will last until surgical samples have been collected. Follow-up data will be collected from the medical record for 90 days following the surgical procedure in order to satisfy the study objectives. Event monitoring will be daily while inpatient and weekly following patient discharge (Figure 3). Adverse events will be assessed daily, including occurrence of SSI, type of SSI, and severity of SSI (Table 6). Serious Adverse events will be reported to the IRB following Mayo Clinic policies and FDA guidances. In the event of a SSI, we will treat and monitor appropriately using standard care procedures which include additional culture testing, drainage, and imaging.

Table 6: Classes of surgical site infections that will be assessed and recorded

Surgical Site Infection Class	Surgical Site Infection definition
Superficial incisional	Only skin and subcutaneous tissue involvement
Deep incisional	Fascia or muscular layers
Organ space	Involvement of any part of the body that was opened or manipulated during the surgical procedure

The overall outcome of the study will be statistically assessed every 2 weeks and any statistically significant differences between the study arms will be reported to the data safety board (p-value < 0.05 for the primary outcome or SSI rate). Criteria for stopping the study will include significantly worse patient outcomes (p<0.05) in Arm 2 of the clinical trial (Table 7), significant deviations from the protocol as determined by IRB, or any other safety issues identified by the data safety monitoring board.

[figure not shown]

Figure 3: A schematic figure of the clinical trial protocol

Table 7: Stopping Rules-Clinical criteria for stopping the clinical trial

Patient Outcome	Criteria for ending the clinical trial
Mortality	Rates of mortality significantly higher in ARM 2 of the clinical trial ($P < 0.05$)
Morbidity	Rates of morbidity significantly high in Arm 2 of the clinical trial ($P < 0.05$)
SSI	Rates of SSI significantly higher in ARM 2 of the clinical trial
Antibiotic adverse events	Number of antibiotic adverse events significantly higher in ARM 2 of the clinical trial ($P < 0.05$)
Pancreatic fistula	Rates of pancreatic fistula significantly higher in ARM 2 of the clinical trial ($P < 0.05$)
Biliary fistula	Rates of biliary fistula significantly higher in ARM 2 of the clinical trial ($P < 0.05$)
Intra-abdominal abscess	Rates of intra-abdominal abscess significantly higher in ARM 2 of the clinical trial ($P < 0.05$)
Pulmonary complications	Rates of pulmonary complications significantly higher in ARM 2 of the clinical trial ($P < 0.05$)
Cardiovascular complications	Rates of cardiovascular complications significantly higher in ARM 2 of the clinical trial ($P < 0.05$)

Data Safety Monitoring Board

The Department of Surgery Data Safety Monitoring Board will be responsible for analysis of the results on a bi-yearly basis (every 6 months) in order to evaluate outcomes as the is enrolling.

